3.4.1.2.1 Data Convention

Central laboratory urine samples for the determination of albumin and creatinine and calculation of UACR will be collected at the timepoints described in the schedule of study procedures in the protocol.

Participants will collect 1st morning void urine samples at home on 3 consecutive days (ideally day of visit and preceding 2 days [refrigerated overnight] which will be returned on the day of visit.

The UACR from each urine sample will be calculated as follows:

$$UACR (mg/mmol) = 10 \times \frac{Urine\ Albumin\ (mg/dL)}{Urine\ Creatinine\ (mmol/L)}$$

At each visit, the geometric mean of the triplicate UACR values will be computed and used for the analysis of UACR. In case of missing values for UACR the geometric mean will be calculated considering the number of the available measurements.

As UACR is assumed to follow a log-normal distribution, it will be log transformed for statistical analysis purposes obtaining the ratio of geometric means.

Percent change from baseline in UACR at $Visit_k$, k in $\{4, 5, 6, 7, 8, 9\}$ will be calculated as:

$$100 \times \left(\frac{GeoMean(UACR_{Visit_k})}{GeoMean(UACR_{Baseline})} - 1 \right)$$

If the urine albumin or urine creatinine lab result is below LOD (level of detection) or LOQ (limit of quantification), impute the missing value using half of the LOD or LOQ, prior to calculating the ratio.

3.4.1.2.2 UACR Baseline

Baseline for UACR will be defined as the geometric mean of 3 consecutive days prior to the Day 1 first dose of study treatment (ideally day of Visit 3 and preceding 2 days). Only samples collected prior to the first dose of study medication will be used. For missing data see the below section on missing data handling.

3.4.1.2.3 Missing Data Handling

In general, missing data will not be imputed.

In the primary MMRM model, all subjects and all data points up to the defined timepoint will be included. No subjects will be excluded because of missing data, and no imputation will be done for missing data.

For intercurrent events, if a subject is lost to follow-up (EOT), discontinues treatment due to AE, or uses prohibited medication, the UACR data on or after intercurrent day are treated as missing. Participants are expected to provide 1st morning void urine samples at home on 3 consecutive days. In case less than 3 values of UACR are available, the geometric mean will be calculated considering the number of the available measurements.

Baseline for UACR will be defined as the geometric mean of at-least 2 measurements of Day1(Visit 3) prior to the day 1 first dose of study treatment. Only samples collected prior to

the first dose of study medication will be used. If Day 1 visit (Visit 3) has less than 2 morning void measurements, and there are 1 or more measurements at Screening (Visit 2), then geometric mean of all morning void UACR measurements from both visits will be used as baseline. If there is only 1 measurement prior to the Day 1 first dose of study treatment (either Day 1 visit (Visit 3) or Screening (Visit 2)), then that measurement will be considered as baseline.

Note: the spot urine (Screening Visit 1) values are excluded from the baseline evaluation.

3.4.1.2.4 Technical details in execution of primary analysis

The execution of the primary analysis model will involve the following four steps:

a) Log-transformation of the UACR:

First, the UACR at baseline and the UACR at post-baseline visits (4, 5, 6, 7, 8, and 9) will be log-transformed. The log-transformed UACR at baseline will then be subtracted from the log-transformed at post-baseline visits to calculate the change of UACR in log units.

b) Execution of the model:

The model will include the change in UACR in log units as a dependent variable and the log-transformed UACR at baseline as covariate, as well as the other independent variables described at the beginning of this section.

c) Back-transformation of the results from the model:

The results from the execution of the model will be back transformed to the original scale after an exponentiation of the LS means to obtain the percent change from baseline of the treatments. The LS mean difference and its CI between each active treatment and placebo will also be back-transformed to yield the percent difference between two treatments with its 90% CI at Visit 10 expressed in percentage.

d) The statistics for the percent change from baseline, percent difference between treatments and percentage 90% CI will be calculated as follows:

- percent change from baseline = $(\exp(\text{estimate})-1)*100$ where estimate is the LS mean
- percent difference between treatments = $(\exp(\text{estimate})-1)*100$ where estimate is the LS mean difference
- 90% CI lower and upper (%): $(\exp(\text{lower})-1)*100$; $(\exp(\text{upper})-1)*100$.

3.4.2 Secondary Efficacy

3.4.2.1 Secondary Efficacy Endpoints

The secondary efficacy endpoints include the following:

- Change from baseline to Day 85 (Week 12) in UACR

3.4.2.2 Secondary Efficacy Analyses

The change from baseline to Day 85 (Week 12) in UACR will be analysed similarly to that of the primary efficacy endpoint based on the Full Analysis Population with the cutoff at Day 85.

3.4.4 Subgroup Analyses

Subgroup analyses for the primary efficacy endpoint by region (Japan versus Rest of the World) and by SGLT2i background will be presented. Descriptive summaries of the primary efficacy variable by treatment group and subgroup will also be produced.

The primary analysis model will be used for subgroup analyses, except that the corresponding randomization stratification factor will not be needed in each model. A forest plot will present the least-squares mean and 90% CI overall and for each subgroup individually.

Additional subgroup analyses may also be performed.

3.4.5 Sensitivity Analyses

The primary endpoint of UACR at Day 169 post baseline time point in Per Protocol Population will be analyzed, as sensitivity analysis, using an analysis of covariance (ANCOVA) adjusting for treatment, baseline log UACR, and randomization stratification factors with last-observation-carried-forward (LOCF) imputation for missing post-baseline measurements. In case the LOCF analysis is needed, some data handling needs to be considered as follows.

Due to two treatment periods, different imputation rules need to be considered for data cut-off at day 85 and all data available beyond day 85,

- If the data at week 12 is missing, the latest respond before week 12 will be carried forward

- If the data at week 24 is missing, the latest response after week 12 will be carried forward

Should be noted that if subject does not have any data after week 12, then that subject will be excluded from the analysis in week 12-24. The data from unscheduled visits will be included together with other available data for endpoint imputation purpose.

Other sensitivity analyses may also be performed.

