3.1.2 Visit Windows

For statistical summaries and analyses by visits, the visits will be mapped based on the actual study days from the first IP dosing date according to the protocol (section 4.2 Table 5 and Table 6) and labelled as Baseline, Day 15, Day 29, Day 57, Day 85, Day 113, Day 141, Day 169, Day 200, and Day 230.

Baseline values will be defined as the last assessment prior to the first administration of study medication (Day 1).

Except the off-treatment visits of the early dropouts (any visit up to including EOT), the visit windows for post-baseline visits will be mapped based on following the table. Any out of window visit will be labelled as unscheduled visit.

Visit (nominal study day)	Visit Window (actual study day)
Baseline ^a	1
Day 15	9-21
Day 29	22-43
Day 57	44-71
Day 85	72-99
Day 113	100-127
Day 141	128-155
Day 169	156-185
Day 200/Follow up	186-215

Visit (nominal study day)	Visit Window (actual study day)
Day 230/Follow up	216-end of study

^aLast assessment prior to first administration of study medication

- If multiple valid assessments fall within the same visit window, the following rules will be applied.
 - If there are two or more valid observations within the same visit window, then the one closest to the scheduled visit will be used in the analysis.
 - If two valid observations are equidistant from the scheduled visit, then the one with the earlier collection date will be used in the analysis.
 - If two valid post-baseline valid observations are collected on the same day, then the one with the earlier collection time will be included in the analysis.
- **For subjects who dropout treatment early**, the follow up visits (any visit after EOT) will be mapped as follows:
 - Determine the last dose visit window based on its actual study day as per the above table. If the last dose was taken up to actual study day 21, then the last dose visit window will be considered as Unscheduled.
 - Any measurement within (\leq) 2 weeks post last dose will be aligned with the last dose visit window.
 - Any measurement beyond ($>$) 2 weeks but within (\leq) 6 weeks post last dose will be aligned with the next protocol scheduled visit window after the last dose visit window. Note: if the last dose visit window is Unscheduled, then the next protocol scheduled visit window should be considered as Day 29.
 - Any measurement beyond ($>$) 6 weeks but within (\leq) 10 weeks post last dose will be mapped as Day 200/Follow up.

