 - Any measurement beyond ($>$) 10 weeks post last dose will be mapped as Day 230/Follow up.

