3.4.1.2 Primary Efficacy Analyses

The primary efficacy endpoint of change from baseline in UACR at Day 169 (Week 24) for each of the MEDI3506 treatment groups compared with the pooled placebo group will be analyzed based on the Per Protocol Population. For the intercurrent events, if a subject is lost to follow-up (EOT), discontinues treatment due to AE, or uses prohibited medication, the UACR data are treated as missing on or after the event and no imputation is performed. The primary analysis will use a mixed model repeated measures (MMRM) analysis with a restricted maximum likelihood (REML) approach without multiplicity adjustment. UACR will be log-transformed before entering the data in the MMRM analysis to alleviate the skewness of the data. The model will adjust for fixed effects of treatment, visit, and treatment-by-visit interaction, randomization stratification factors, baseline log UACR and baseline log UACR-by-visit interaction. Randomization stratification factors are with SGLT2i background or not, in Japan or rest of world.

To allow generality for the covariance structure for the repeated measures, the variance-covariance matrix will be assumed to be unstructured, i.e., purely data dependent, to model within subject errors. If the unstructured variance-covariance matrix will not fit, i.e., fail to converge, the following covariance structures will be utilized in the order of 1) heterogeneous toeplitz, 2) heterogeneous autoregressive of order 1, and 3) heterogeneous compound symmetry. The first (co)variance structure which does not have a convergence problem will be the one used for the analysis. If a structured covariance has to be used, the “sandwich” estimator of the variance covariance matrix of the fixed effects parameters will be used in order to deal with possible model misspecification of the covariance matrix. The denominator degrees of freedom will be calculated according to the Kenward-Roger method. Additionally, there will be no adjustment for multiplicity.

If none of the above models converge, the analysis will be altered to use an analysis of covariance (ANCOVA) with last observation carried forward (LOCF) imputation method implemented. Details of this analysis is provided in the [Section 3.4.5](#) for sensitivity analysis.

Additionally, all collected values of UACR will be listed.

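### The one specified sensitivity analysis for Week 24 UACR, also the fallback primary, is LOCF in the same Per Protocol set and gives little information on the missing-at-random assumption

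*SAP*

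**What the plan says.** **Primary analysis (SAP 3.4.1.2, 3.4.1.2.3).** An MMRM on log UACR in the Per Protocol Population. UACR is blanked from the day of loss to follow-up, AE discontinuation or prohibited medication, and nothing is imputed.

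**Sensitivity analysis (SAP 3.4.5).** The population and endpoint are those of the primary: "The primary endpoint of UACR at Day 169 post baseline time point in Per Protocol Population will be analyzed, as sensitivity analysis". The method is an ANCOVA "with last-observation-carried-forward (LOCF) imputation for missing post-baseline measurements". For Week 24 the rule is "If the data at week 24 is missing, the latest response after week 12 will be carried forward", and "if subject does not have any data after week 12, then that subject will be excluded from the analysis in week 12-24". The section ends with "Other sensitivity analyses may also be performed" and names none.

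**Fallback primary (SAP 3.4.1.2).** If the unstructured covariance matrix and all three listed alternatives fail to converge, "the analysis will be altered to use an analysis of covariance (ANCOVA) with last observation carried forward (LOCF) imputation method implemented". Section 3.4.5 is cited for the details.

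**Analysis sets (SAP 3.2, Table 2; 3.3.2).** The Per Protocol Population requires dapagliflozin after Week 12 and no relevant important deviation. Relevant deviations include prohibited medication, more than one missed visit, and absent UACR samples. Table 2 assigns efficacy analyses to the Full Analysis Population, but section 3.4 describes no Week 24 UACR analysis in it.

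**Visit labels for early stoppers (SAP 3.1.2).** Visits after end of treatment are labelled by time since last dose. A measurement more than 6 and up to "10 weeks post last dose will be mapped as Day 200/Follow up". One more than "10 weeks post last dose will be mapped as Day 230/Follow up".

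**The concern.** Once post-event data are blanked and left to the MMRM, the estimate assumes that the missing values behave like those of comparable subjects still observed in the same arm. That cannot be verified from the data. A sensitivity analysis has to vary the assumption and show how far it can move before the conclusion changes.

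The LOCF ANCOVA does not do this:

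- It replaces one untestable assumption with another single one, that the last value persists to Week 24.
- It enters the carried value as if measured, with no allowance for imputation uncertainty.
- It works on nearly the same observed data as the MMRM, because it can fill a Week 24 gap only for a subject who already has UACR after Week 12.

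If the two analyses agree, a reader may conclude that the result is robust to missing data when that has hardly been examined. If the fallback is triggered, the primary and the sensitivity analysis are the same analysis.

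**Working it through.** **1. The SAP's own figures (section 2.4).** Inputs: 30% reduction, SD 1.0 on the log scale, one-sided alpha 0.05, evaluable 125 versus 125 (300 mg) and 85 versus 125 (other arms).

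- δ = ln(1/0.7) = 0.3567
- Power = Φ(δ / √(1/n₁ + 1/n₂) − 1.645)
- 125 vs 125: SE = √(2/125) = 0.1265; Φ(2.820 − 1.645) = 88.0%
- 85 vs 125: SE = √(1/85 + 1/125) = 0.1406; Φ(2.537 − 1.645) = 81.4%

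These agree with the stated at least 85% and 80%. The sample-size calculation is not in question.

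**2. Who can contribute a Week 24 value to the LOCF analysis?**

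| Subject | Contribution at Week 24 |
|---|---|
| Never received dapagliflozin | None; outside the Per Protocol Population (Table 2) |
| Per Protocol, no UACR after Week 12 | None; dropped by section 3.4.5 |
| Per Protocol, UACR after Week 12 but none at Week 24 | Last value after Week 12, treated as observed |
| Per Protocol, UACR at Week 24 | Observed value, as in the MMRM |

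Only the third row has an imputed Week 24 value. The SAP does not say how many subjects that is.

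**3. Illustration of size.** Assume a share m of an active arm in fact has no effect versus placebo, and the rest have the planned effect. The diluted log effect is (1 − m) × 0.3567. Power uses all randomized subjects: 140 vs 140, and 95 vs 140.

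| m | Log effect | Reduction | Power, 300 mg | Power, other arms |
|---|---|---|---|---|
| 10% (the SAP's dropout figure) | 0.321 | 27.5% | 85.1% | 77.9% |
| 20% (assumption) | 0.285 | 24.8% | 77.1% | 69.2% |

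**4. What a tipping-point analysis would show.** Suppose the observed reduction is 30% and a share m is missing in each arm, so SE = √(1/[n₁(1−m)] + 1/[n₂(1−m)]). Significance is lost when the missing active-arm values are worse than missing at random predicts by a log shift of (0.3567 − 1.645 × SE)/m.

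| m | 300 mg: SE, shift, UACR ratio | Other arms: SE, shift, UACR ratio |
|---|---|---|
| 10% | 0.126, 1.494, 4.5 | 0.140, 1.262, 3.5 |
| 20% | 0.134, 0.684, 2.0 | 0.149, 0.561, 1.75 |

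**5. Visit labels for a sample taken on Day 169 by an early stopper (section 3.1.2).**

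| Last dose on day | Days since last dose | Label |
|---|---|---|
| 98 or earlier | 71 or more | Day 230/Follow up |
| 99 to 126 | 70 to 43 | Day 200/Follow up |
| 127 | 42 | Day 141 |
| 128 or 141 | 41 or 28 | Day 169 |

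Such a sample, if taken, is labelled follow-up whenever the last dose was more than 42 days earlier. This matters for any analysis that is meant to use all observed Week 24 data.

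**The case against.** Much of the other side's case stands.

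- **LOCF is not missing at random.** A reader might infer that the assumption is never tested. That is too strong: LOCF is a different, if poor, assumption, and section 3.4.5 permits further unnamed analyses. What is absent is a specified, structured departure.
- **The exclusion rule removes few subjects.** The Per Protocol Population already requires dapagliflozin after Week 12. Within LOCF, declining to carry a pre-dapagliflozin value into the dapagliflozin period is sensible.
- **The relabelling hardly touches the primary analysis.** A reader might infer that real Week 24 outcomes are being discarded on a large scale. Sections 3.4.1.2 and 3.4.1.2.3 already blank the data after the three listed events. The SAP does not show whether early stoppers give a Day 169 sample; that depends on the protocol.
- **The 10% dropout cannot be read as the share filled by LOCF.** It includes subjects who left too early for the rule to apply, so no bias figure for LOCF follows from it.
- **At 10% missing the result is hard to overturn.** Ratios of 3.5 to 4.5 are large departures. At 20% they fall to 1.75 to 2.0, but 20% is not the SAP's figure.
- **The fallback is remote.** Four covariance structures must fail with six post-baseline visits and about 505 evaluable subjects.

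None of this makes LOCF an informative check on the primary analysis.

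**Conclusion.** The point holds in a limited form. The one specified sensitivity analysis for Week 24 UACR is a single-imputation LOCF ANCOVA in the same Per Protocol set, and it doubles as the fallback primary. It contains no structured departure from missing at random, so agreement with the MMRM would say little about that assumption.

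The size is illustrative: 30% becomes 27.5% if 10% of the active arm has no effect, and 24.8% if 20% does. These figures show what dilution would do to the effect. They are not estimates of bias in the MMRM or in the LOCF analysis, and the share of missing Week 24 values within the Per Protocol set cannot be derived from the SAP.

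The documents do not show that the primary conclusion would be wrong. At the stated dropout it may well be robust, but the plan specifies no analysis that would demonstrate this. The change should be made because it is cheap and answers the question that the present analysis leaves open.

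**What to change.** 1. **Replace the LOCF sensitivity analysis** with a delta-adjusted (tipping-point) or reference-based multiple imputation in the primary analysis set. Keeping population and event handling unchanged isolates the missing-data assumption.
2. **Add a supplementary Week 24 analysis in the Full Analysis Population** using all observed UACR regardless of intercurrent events. This changes the population and the event strategy together, so it answers a different question and should be labelled accordingly. Assign visits by actual study day for everyone in this analysis. How much post-discontinuation data it gains depends on what was collected.
3. **If reference-based imputation is used in the Full Analysis Population**, state how subjects who never started dapagliflozin are handled. The placebo arm receives it from Week 12, so copying or jumping to placebo would credit its effect to subjects who never took it.
4. **Replace the LOCF fallback primary** with multiple imputation followed by ANCOVA at Day 169.

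Cost: SAP wording, modest programming and two further outputs. Item 1 needs no data beyond those already planned for the primary analysis.

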3.4.6 Japan Specific Analysis

A subset of the planned outputs will be repeated for participants from Japan, as required for interaction with the Japanese Regulatory Agency. The outputs will be identified in the SPP.

3.5 Pharmacodynamic Analyses

3.5.1 Pharmacodynamic Endpoint(s)

CCI

3.5.2 Analysis of Pharmacodynamic Endpoint(s)

Percent change from baseline to Day 85, and Day 169 will be analysed in both per protocol population and full analysis population.

The MMRM model will be used adjusting for treatment, baseline, and randomization stratification factors.

3.6 Safety Analyses

The analyses of the safety endpoints will be performed using the Safety Analysis Population for data cut-off at day 85 and all data available beyond day 85. The evaluations will be descriptive in nature, and observed differences will be evaluated for medical relevance. No formal statistical comparisons will be performed for the safety summaries.

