The study was started in November 2019 as a Phase 2a study and it was paused due to COVID-19 pandemic by March 2020. It was resumed in July 2020, and then endured several amendments where additional doses of MEDI3506 and the add-on of Dapagliflozin in the second half of the 6-month treatment period are introduced. Therefore, the study consists of two periods, where Period 1 is without Dapagliflozin and Period 2 is with Dapagliflozin. Accordingly, several cohorts of participants can be defined upon the evolution of the trial design as illustrated in [Table 1](#). Cohort 1 which are divided in two groups a and b, are subjects who have started on the Phase 2a. Cohort 1a participants were discontinued and did not have the opportunity to complete 6-month treatment due to COVID-19 pandemic. Participants in Cohort 1b were enrolled after the study was re-started and had the opportunity to complete 6-month treatment. These subjects will continue on treatment with MEDI3506/placebo without dapagliflozin. About 24 participants were randomized in Cohort 1 and 19 of them were discontinued when the study was paused. Cohort 2 are subjects who have started on the Phase 2a study but have not completed 12 weeks of treatment prior to Amendment 2. They were transitioned to the Phase 2b study and given dapagliflozin starting on Day 85 (Week 12). Finally, Cohort 3 are subjects who will enrol in ongoing Phase 2b study.

Table 1: Cohort of study participant by randomization scheme and active treatment regiment

Cohort	Randomization Scheme 1 (R1)	Randomization Scheme 2 (R2)	Active Treatment Regiment	
			6-month MEDI3506 monotherapy	MEDI3506 mono in 1 st 3 mons, MEDI3506 + Dapa in 2 nd 3 mons.
1a*	X		X	
1b*	X		X	
2	X			X
3		X		X

R1 = Randomization scheme for MEDI3506 60 mg, 300 mg, and matching placebo; R2 = Randomization scheme for MEDI3506 30 mg, 60 mg, 120 mg, 300 mg, and matching placebo.

* Participants in Cohort 1a were discontinued and did not have the opportunity to complete 6-month treatment due to COVID-19 pandemic. Participants in Cohort 1b were enrolled after the study was re-started and had the opportunity to complete 6-month treatment.

Should be noted that the method and the analysis details described in this document will be considered for Cohort 2 and 3. Cohort 1 will be summarized separately with some descriptive summary statistics and listing.

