2.1.2 Secondary Study Objectives

- 1) To evaluate the effect of MEDI3506 as measured by change from baseline in urine albumin:creatinine ratio (UACR) at Week 12, when compared to placebo.
- 2) To evaluate safety and tolerability of MEDI3506 between Period 1 and 2 in subjects with DKD
- 3) To describe the PK and immunogenicity of MEDI3506 in subjects with DKD
- 4) To evaluate the effect of MEDI3506 in combination with ACEi or ARB between Period 1 and 2 on albuminuria in subjects with DKD

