2.2 Study Design

This is a Phase 2b, randomized, double-blind, placebo-controlled, multi-center study to evaluate the efficacy, safety, PK, and immunogenicity of MEDI3506 in adult subjects with DKD. Approximately 565 subjects from around 130 study sites among multiple countries will be randomized (95:95:95:140:140) to MEDI3506 30, 60, 120, or 300 mg, or volume-matched placebo dosed subcutaneously (SC) every  days over a 168-day (24-week) treatment period.

Assuming 10% dropout, this will allow approximately 505 evaluable subjects to complete the study. The study includes a screening period of up to 35 days (Day -37 to Day -3), a 168-day (24-week) treatment period, and a 70-day (10-week) follow-up period. The study periods are shown in Figure 1.

Figure 1: Study Flow Diagram

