3 STATISTICAL METHODS

3.1 General Considerations

3.1.1 Data Presentation

Data will be presented in data listings sorted by treatment group, subject number and date collected, where appropriate. Tabular summaries will be presented for each treatment with the placebo groups for volume matching combined. Categorical data will be summarized by treatment group with the number and percentage of subjects within each category.

Continuous variables will be summarized by treatment group with descriptive statistics including mean, standard deviation, median, minimum, and maximum. Baseline values will be defined as the last valid assessment prior to the first administration of investigational product unless otherwise specified.

All statistical tests will be 2-sided at an $\alpha = 0.10$ significance level unless stated otherwise. There will be no adjustment for multiplicity.

Data analyses will be performed using SAS[®] version 9.4 or higher (SAS Institute Inc., Cary, NC). The analytical results generated from SAS programs will follow AstraZeneca/MedImmune SAS programming standards and will be validated according to AstraZeneca/MedImmune SAS validation procedures.

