3.6.1 Adverse Events and Serious Adverse Events

Adverse events will be coded with MedDRA version 22.0 or later. Analysis of adverse events will include the type, incidence, severity and relationship to study investigational product summarized by MedDRA System Organ Class (SOC) and Preferred Term (PT), by treatment group as well as MEDI3506 overall. Treatment emergent adverse event is defined as any AE reported after the first IP up to the wash-out of MEDI3506 (5 half-lives: 90 days after the last dose of IP). If an AE is reported the day of the first IP (ie. Day 1) with a missing time, this AE will be considered as treatment emergent. The AEs summaries will include only treatment-emergent AEs (TEAE), i.e., those starting after the first administration of double-blind investigational product. Subjects will be counted once for specific PT or MedDRA SOC when calculating incidence rates. If the same AE Preferred Term occurs multiple times within a subject, the highest severity and level of relationship observed will be reported. Non-treatment-emergent AEs/serious adverse events (SAEs), i.e., those AEs with onset after screening but before the start of double-blind treatment will be presented in the listings. All TEAEs related to dapagliflozin will also be summarized. For subjects testing positive for COVID-19, overall summary of AEs, AEs by PT and SOC, summary of SAEs, AESI and the proportion of asymptomatic subjects will be provided.

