Progression of heart failure	No clinically meaningful imbalance in HF-related AEs	Clinically meaningful increased frequency of HF-related AEs (5 – 10 patients more than placebo)*	Dose-dependent meaningful increase of hospital admissions for HF (>10 patients on highest dose than placebo)* or a relatively increased frequency (3 – 5 patients more than placebo)* of deaths due to HF that impacts on benefit/risk evaluation of MEDI3506

* The cut-off target patient numbers presented in the criteria above should be used as an approximation and interpreted in context of the overall B/R profile of MEDI3506

The number, percentage and percentage per patient exposure year (PEY) of participants reporting TEAEs in each treatment group will be tabulated by system organ class and preferred term; by system organ class. A summary of adverse events in any category will be presented by treatment. The incidence of common ($\geq 5\%$ of participants in any treatment group) TEAEs, common treatment-emergent serious AEs (TESAE), and AEs leading to discontinuation of study medication will be summarized by system organ class, preferred term and treatment group, sorted in decreasing overall (across treatments) frequency. Moreover, TEAEs leading to hospitalization will also be presented.

Listings will be presented of participants with SAEs, AEs leading to discontinuation, and participants who died. A listing will be presented of participants with AEs, detailing whether these are SAEs, AEs leading to discontinuation, or result in death.

Summary statistics of laboratory data will be presented. Participants with laboratory values which are highlighted as abnormal will be listed. Summary statistics of vital signs data may be collected.

SIGNATURE PAGE

This is a representation of an electronic record that was signed electronically and this page is the manifestation of the electronic signature

Document Name: d9183c00001-sap-ed-6		
Document Title:	Statistical Analysis Plan Edition 6	
Document ID:	Doc ID-004810933	
Version Label:	6.0 CURRENT LATEST APPROVED	
Server Date (dd-MMM-yyyy HH:mm 'UTC'Z)	Signed by	Meaning of Signature
05-Jul-2023 20:20 UTC	PPD	Content Approval

Notes: (1) Document details as stored in ANGEL, an AstraZeneca document management system.

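### The final AE tables give crude percentages over unequal time spans before and after Day 85, so they cannot support the Period 1 versus Period 2 safety objective

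*SAP*

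**What the plan says.** Secondary objective 2 (SAP Section 2.1.2) is "To evaluate safety and tolerability of MEDI3506 between Period 1 and 2 in subjects with DKD". The Introduction defines the periods by add-on treatment: "Period 1 is without Dapagliflozin and Period 2 is with Dapagliflozin", with dapagliflozin introduced in the second half of the six-month treatment period.

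Section 3.6 implements this as analyses "performed using the Safety Analysis Population for data cut-off at day 85 and all data available beyond day 85". It gives no end to the later set and no percentage base for it. It also does not say whether Day 85 means a fixed study day or the Week 12 visit.

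For adverse events, Section 3.6.1 states: "Subjects will be counted once for specific PT or MedDRA SOC when calculating incidence rates". The general format in Section 3.1.1 is the "number and percentage of subjects within each category". Treatment-emergent events are accepted until 90 days after the last dose. Section 2.2 gives "a 168-day (24-week) treatment period, and a 70-day (10-week) follow-up period", so events in follow-up fall in the later set.

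An exposure-adjusted measure appears only in Appendix A 3, for the interim safety set, where the "percentage per patient exposure year (PEY) of participants reporting TEAEs in each treatment group will be tabulated". Section 3.6 and its subsections do not carry it into the final tables.

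**The concern.** A once-per-subject percentage grows with the time over which the subject is watched. If the two sets differ in length, their percentages differ even when the event rate is the same in both. Section 3.6 plans no formal tests but says that observed differences will be judged for medical relevance. A reader who sets the two columns side by side, as objective 2 invites, could take a difference produced by observation time for a change in tolerability once dapagliflozin is added. If the rate really falls after the first weeks, the longer second set could hide that fall.

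The later set also mixes two phases. By the Introduction's definition Period 2 is the second half of treatment, yet data beyond Day 85 include the weeks after treatment has ended.

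**Working it through.** The SAP states no safety incidence and no period length, so there is no plan figure to reproduce. Incidence levels and the constant hazard below are assumptions for illustration.

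**Inputs from the SAP**
- Split at Day 85 (Section 3.6): first set = 85 days.
- Last nominal visit Day 230 (Section 3.1.2): second set = 230 − 85 = 145 days; ratio 145/85 = 1.71.
- Alternative end from Section 2.2: 168 + 70 = 238; second set = 238 − 85 = 153 days; ratio 1.80.
- Nominal end of treatment Day 169: 230 − 169 = 61 of the 145 days (42%) are post-treatment.
- The 90-day event window does not shorten this for completers. The dosing interval is redacted; with an assumed last dose between Day 141 and Day 169, the window closes between Day 231 and Day 259.

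**Formula.** If I1 is the Period 1 incidence, the daily hazard is h = −ln(1 − I1)/85, and incidence over a set of L days is 1 − exp(−hL) = 1 − (1 − I1)^(L/85). This takes full follow-up and one count per subject within each set.

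For I1 = 10%, L = 145: 1 − 0.90^(145/85) = 16.5%. For I1 = 30%: 1 − 0.70^(145/85) = 45.6%.

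| Assumed Period 1 | Day 86–230 (145 d) | Day 86–238 (153 d) | Cumulative, Day 1–230 | Day 86–169 only (84 d) |
|---|---|---|---|---|
| 5% | 8.4% | 8.8% | 13.0% | 4.9% |
| 10% | 16.5% | 17.3% | 24.8% | 9.9% |
| 20% | 31.7% | 33.1% | 45.3% | 19.8% |
| 30% | 45.6% | 47.4% | 61.9% | 29.7% |

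The hazard is the same in both periods in every cell; the differences come from length alone.

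**Sensitivity to the denominator.** Section 2.2 assumes 10% dropout for the whole study. Suppose, as an extreme, that all of it occurred before Day 85 and those subjects stayed in the Period 2 denominator. Then 10% becomes 0.9 × 16.45% = 14.8%. Departures therefore offset part of the artefact but do not remove it.

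**Check of the remedy.** With time at risk counted to the first event, the rate at I1 = 10% is −ln(0.90)/85 × 365.25 × 100 = 45.3 per 100 patient-years in both periods. With each subject's whole period as exposure, it is 0.10 × 365.25/85 = 43.0 per 100 patient-years in Period 1 and 0.1645 × 365.25/145 = 41.4 in Period 2, so nearly equal. At 30% the same sums give 128.9 and 114.8, so time to first event is the cleaner base for common events. Ending Period 2 at Day 169 also removes the length artefact from the crude percentages (last column).

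**The case against.** The strongest reply is that safety is descriptive, that events are tabulated by treatment group, and that objective 2 concerns MEDI3506 rather than dapagliflozin. The randomised comparison with placebo within a period is not biased by how long the period is. That stands, and it confines the point to the between-period reading of AE incidence tables. Laboratory, vital-sign and ECG summaries by visit are outside it. It does not remove the point, because the objective itself is worded as between periods.

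The hazard may not be constant, since adverse events can cluster after first dosing. That also stands: the table shows what length alone does, not what the trial will find. Even exposure-adjusted, a before-and-after contrast remains confounded with time on study and with loss of susceptible subjects.

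The SAP also summarises TEAEs related to dapagliflozin. This helps in part, but it rests on causality assessment and does not equalise the periods.

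Three stronger readings are tempting and not supported:
- *That the Period 2 denominator is wrong.* Section 3.6 names the analysis population but states no percentage base for the later set, and table templates sit in a separate programming plan. The base is unstated, not shown to be wrong.
- *That up to two weeks of each subject's events fall in the wrong period.* The 72–99 range in Section 3.1.2 maps assessments to visits; it is not an attendance rule. It gives an outer bound of 13 days before to 14 days after Day 85, not an expected size. If Day 85 means the visit, most of this disappears.
- *That the Week 12 UACR endpoint is affected.* It has its own analysis in Section 3.4.2.2, and nothing here bears on it.

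**Conclusion.** The concern holds in limited form. As written, the final AE tables compare 85 days with about 145 days (ratio 1.7; 1.8 if follow-up runs to Day 238), with about 42% of the later span after nominal end of treatment. Crude once-per-subject percentages from those sets cannot support the between-period contrast in secondary objective 2. For assumed Period 1 incidences of 5% to 30%, length alone multiplies the Period 2 figure by 1.68 down to 1.52 under a constant hazard. If the second set is cumulative to Day 230, 10% becomes 24.8%. Section 3.4.5 uses similar wording with rules that separate data before and after Week 12, which favours the disjoint reading, but Section 3.6 does not settle it.

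These sizes rest on assumed incidences, a constant hazard and near-complete follow-up. The direction of the length effect does not depend on the incidence chosen. The SAP already contains a suitable measure and confines it to the interim, so the change should be made.

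**What to change.** In Sections 3.6 and 3.6.1:

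1. Report exposure-adjusted incidence by arm and period in the final AE tables, beside n and %. Use the PEY measure from Appendix A 3, and state whether exposure stops at the first event.
2. State that the two sets are disjoint. End Period 2 at end of treatment and tabulate post-treatment follow-up TEAEs separately. Say which set receives events in a subject who stopped treatment before Week 12 but remains in follow-up.
3. Use as the Period 2 denominator the subjects still under observation at its start.
4. Define the boundary as each subject's actual Week 12 visit, the planned dapagliflozin start, with a fallback for a missed visit.
5. Add a supplementary summary by actual dapagliflozin receipt. It should stay supplementary: receipt is a post-randomisation event, and two strata enter with SGLT2i background, so dapagliflozin start is not a clean exposure boundary for them.

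The cost is SAP wording and extra table columns. Items 1 to 4 need event onset, visit and dosing dates. Item 5 needs dapagliflozin receipt, which the Per Protocol definition in Section 3.2 already requires to be known.
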